1. Total Suturing time for mesh placement = time from insertion of Y mesh or first flat mesh arm into pelvis to last sacral suture placed
2. Total OR time = operating room time of entry and exit
3. Total Case time = Incision to end of closure

Secondary Outcomes:

1. Intraoperative, peri-operative and post-operative complications
2. Hospital costs (Y mesh v. dual mesh and stratified by RA LSC v. LSC)
3. Post-operative patient outcomes at 6 weeks, 6 months, 12 months and 24 months
 - Pelvic Organ Prolapse Quantification (POPQ) system (standardized quantification of prolapse established by the International Continence Society) – Required at 6 months; Optional but encouraged at 12 and 24 months.
 - Pelvic Floor Dysfunction Inventory (PFDI-20) – Required pre-operatively and at 6 weeks, 6, 12 and 24 months.

Study Population: Study subjects will be recruited from patients that present to the Center of Urogynecology and Pelvic Floor Disorders in the Department of Obstetrics and Gynecology at the Cleveland Clinic main campus, Hillcrest Hospital and Fairview Hospital, and their surgeries will be performed at either one of these sites.

Inclusion Criteria:

- Age \geq 18, who are to undergo laparoscopic or robotic laparoscopic sacrocolpopexy for pelvic organ prolapse
- Other concomitant laparoscopic or prolapse and anti-incontinence procedures (e.g., laparoscopic supracervical hysterectomy, cystocele repair, rectocele repair or mid-urethral sling procedures) will be performed at the primary surgeon's discretion.

Exclusion Criteria:

- Inability to comprehend written and/or spoken English
- Inability to provide informed consent
- Medical illness precluding laparoscopy
- Need for concomitant surgeries not related to pelvic organ prolapse or incontinence
- Sacrocolpoperineopexy

Study Procedures:

Study Identification and Recruitment

Potential subjects will be identified by members of the Center for Urogynecology and Pelvic Reconstructive Surgery at the Cleveland Clinic main campus and Fairview Hospital. Eligible patients that agree to participate will be provided written informed consent administered by the collaborators listed on this IRB at the Cleveland Clinic main campus and Fairview Hospital.

Randomization

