- 6-week postoperative visit: PFDI-20
- 6-month postoperative visit (Required): POP-Q exam (performed by a provider blinded to the mesh used at the time of the procedure)
- 12 month, 24 month postoperative visit (Optional): POP-Q exam (performed by a provider blinded to the mesh used at the time of the procedure)
- 6-month, 12-month, 24-month postoperative visit: PFDI-20

- At 6, 12 and 24-months: Review of electronic medical record (inpatient notes, d/c summary, ER visits), assessing for postoperative complications
 - Reoperation for immediate complications = reoperation within 30 days of surgery
 - Abdominal Wound infection = fascial, subcutaneous, cutaneous infection requiring antibiotic treatment
 - Hematoma = intrapelvic/abdominal
 - Vaginal cuff cellulitis/Pelvic Abscess = requiring IV/PO antibiotic therapy and/or transvaginal, transgluteal or percutaneous drainage
 - DVT/PE = diagnosed with Doppler US or CT scan
 - Reoperation for SUI with pubovaginal sling (synthetic or fascial), colposuspension, injection with periurethral bulking agents
 - Reoperation for mesh exposure
 - Reoperation for recurrent POP
 - Bowel Injury/Bowel Obstruction = enterotomy, perforation, ileus, partial/complete obstruction
 - Port site or incisional hernia
 - Need for any radiologic imaging
 - Lower urinary tract injury = bladder, ureteral
 - Neurologic Injury = brachial plexus, abdominal wall (ilioinguinal, iliohypogastric), lower extremity (femoral, sciatic, common peroneal)
 - Pulmonary complications = pneumonia, pulmonary hypertension, pulmonary edema within 14 days of surgery
 - Cardiac = ACS, MI, HF within 14 days of surgery
 - Postoperative ICU admission

[figure not shown]
Protection of each subject's personal health information will be a priority in this study. One master excel file containing subject personal information including name and medical record number will be kept in a password-protected file, on a designated protected research drive on a password-protected computer in a locked office at the Cleveland Clinic. In that file, each subject will be assigned a subject identification number that will be used for the purposes of data collection in order to de-identify subjects.

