We will use descriptive statistics to show our demographic and baseline data: categorical variables will be presented as n/N (%) with 95% confidence intervals and continuous variables will be presented as mean+/-SD [range]. Y mesh and dual mesh will be compared between the two groups (Y mesh LSC + RA LSC v. Dual mesh LSC + RA LSC). With a continuous outcome and two categorical independent factors, a two-way

analysis of variance will be used to evaluate differences between the groups. The results will be presented in a standard ANOVA table, which should be sufficient to determine if differences exist. A linear regression will be done to demonstrate actual changes in surgical time attributed to each variable. We will control for LSC ASC and RA LSC ASC by performing a logistic regression. Cost utility analysis will be used to compare the differential mean operating room costs with incremental cost effectiveness ratios (ICERs) calculated as appropriate.

Summary of tasks for study:

	Preop	O R	6 wk postop	6 mo f/u	12 mo f/u	24 mo f/u
Informed consent	X					
Demographic data	X					
Randomization	X					
PFDI-20	X		X	X	X	X
POP-Q	X			X	X ¹	X ¹
OR data collection sheet		X				
Review of d/c summary, chart, postop Hct, complications (ER visits, etc)			X	X	X	X

1. **POP-Q – Optional but encouraged at 12 and 24 months.**

References:

3. Porges RF & Smilen SW. Long term analysis of the surgical management of pelvic floor support defect. *Am J Obstet Gynecol* 1994;171:1518–1528.
4. Birch C. The use of prosthetics in pelvic reconstructive surgery. *Best Pract Res Clin Obstet Gyn* 2005;19(6):979-991.
5. Chu CC & Welch L. Characterisation of morphological and mechanical properties of surgical mesh fabrics. *J Biomed Res* 1985;19:903–916.
6. Kaupp HA, Matulewicz TJ & Lattimer GL. Graft infection or graft reaction? *Arch Surg* 1979;114:1419-1423.

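### The complication list records mesh exposure only as a reoperation, so an exposure managed without surgery has no item and would be undercounted within secondary outcome 1

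*Combined protocol and SAP*

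**What the plan says.** Secondary Outcomes, item 1, is broad: "Intraoperative, peri-operative and post-operative complications". It does not mention mesh exposure.

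The postoperative part of Data Collection & Management gives the list of complications to look for at 6, 12 and 24 months. Its one mesh-specific entry is "Reoperation for mesh exposure". The stated method is "Review of electronic medical record (inpatient notes, d/c summary, ER visits), assessing for postoperative complications".

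The same section requires one vaginal examination after surgery: "6-month postoperative visit (Required): POP-Q exam (performed by a provider blinded to the mesh used at the time of the procedure"). At 12 and 24 months the examination is optional. Exposure is not named as a finding to record at any of the three.

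The task table (Summary of tasks for study) words the review a little more widely, "Review of d/c summary, chart, postop Hct, complications (ER visits, etc"), and marks it at 6 weeks as well as at 6, 12 and 24 months.

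**The concern.** A reoperation is a management decision that follows an exposure; it is not the exposure. If some exposures are observed or treated without surgery, a count of reoperations is lower than the count of exposures. An exposure found by the blinded examiner at the required 6-month visit could leave no trace in the complication data.

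What is at stake is how a low count is read. A report of 0/30 for this item would mean that no woman was reoperated for exposure, and a reader could easily take it to mean that no exposure occurred. In a comparison of two mesh grafts, that is a safety result that readers will look for.

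**Working it through.** **Text check.** How the list and the rest of the plan treat comparable events:

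| Event | How listed | Second measure in the plan |
|---|---|---|
| Hematoma | by occurrence | not needed |
| Hernia ("Port site or incisional hernia") | by occurrence | not needed |
| Abdominal wound infection | infection that required antibiotics | none |
| Recurrent prolapse | reoperation | POP-Q |
| Mesh exposure | reoperation | none |

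No other part of the document mentions exposure. The sources named with the list are inpatient notes, discharge summary and ER visits. Office notes, where a finding at a follow-up visit would normally be written, are not among them. The task table's reference to the chart could include them but does not say so.

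**Direction.** Recorded count = true count × share reoperated. The recorded count is lower whenever that share is below 1. No exposure rate is needed for this step.

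**Size, as an illustration.** The plan gives neither an exposure rate nor the share reoperated, so there is no figure of its own to reproduce here. The only input from the documents is enrolment (Analysis Plan): 15 × 4 = 60 women, or 30 per mesh if balanced. The rest is assumed: true rate p, share reoperated f, all 60 followed, and every exposure detected.

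- Expected recorded count = 60 × p × f
- Chance of recording none = (1 − p × f)^60

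| Assumed p | f = 1 (all exposures counted) | f = 0.5 | f = 0.25 |
|---|---|---|---|
| 2% | 1.2 expected; none 29.8% | 0.6; 54.7% | 0.3; 74.0% |
| 5% | 3.0; 4.6% | 1.5; 21.9% | 0.75; 47.0% |
| 10% | 6.0; 0.2% | 3.0; 4.6% | 1.5; 21.9% |

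At p = 5%, counting every exposure gives 0.95^60 = 4.6%. With half reoperated, p × f = 0.025 and 0.975^60 = 21.9%.

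**The case against.** The case on the other side has four parts.

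- **The entry is not a definition of exposure.** Where the list defines a term it uses an equals sign, and this entry has none. It counts correctly what it names. A reader might infer that the protocol defines exposure as reoperation, so that a non-operated exposure cannot be a complication. The documents do not support that. The list is not declared exhaustive, secondary outcome 1 is worded generally, and the task table adds chart review. The REDCap data dictionary is not among the documents, so the actual form fields are unknown. This stands: ad hoc capture is possible. But nothing prompts it, so it would depend on who reviews the record.
- **Exposure is not singled out.** Wound infection and cuff cellulitis or abscess carry treatment thresholds, and stress incontinence and recurrent prolapse are listed by reoperation. This stands, and it limits the contrast to hematoma and hernia. Recurrent prolapse differs because the POP-Q measures it separately.
- **Numbers are small and no exposure hypothesis is stated.** This also stands. With 0 of 30 in one group, the two-sided 95% upper limit is 1 − 0.025^(1/30) = 11.6%, so even a complete count could not exclude a sizeable rate. That limit reflects the sample size, not the wording of the item. It argues for descriptive reporting, not for leaving out exposures that are seen.
- **Reoperation can be found in records when the optional examinations are missed.** The documents do not give this as a reason, but it is a fair reason to keep reoperation as a sub-item.

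**Conclusion.** The point holds in a limited form. Following the list as written would undercount mesh exposures within secondary outcome 1, provided that some exposures are managed without reoperation. The amount cannot be derived from the documents. The rise from 4.6% to about 22% in the chance of recording none rests on an assumed 5% rate, half reoperated, complete follow-up of 60 women and full detection; the other cells of the table show how far it moves.

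A reader might go further and infer that the plan conceals a safety difference between the grafts, or that exposure is the main mesh-specific complication. The documents support neither. They show only that it is the sole mesh-specific item listed, and they give no basis for expecting the undercount to differ between the meshes. A report of no reoperations for exposure would be true; it would mislead only if restated as no exposures.

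The effect is confined to part of a secondary outcome that 30 women per mesh can support only descriptively. Suturing time, the other primary outcomes and the sample size are untouched. This is a minor, cheap improvement.

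**What to change.** 1. Replace the list entry with an item for any mesh exposure, whether found on examination or in the record including office notes, with its management recorded. Keep reoperation for exposure as a sub-item.
2. Add a yes/no mesh-exposure field to the blinded POP-Q form at 6 months, and at 12 and 24 months when the examination is done.
3. Report the counts descriptively by mesh, with the number examined at each visit as the denominator.

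The cost is one broadened item, one form field and a wider record source, with no new visit and no change in sample size. There are two downsides. Reported complication rates may be higher than under the present list, and the 12- and 24-month counts will depend on who attends the optional examinations, which is why the number examined must be shown.

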All subjects will be predetermined by their surgeon to undergo either a laparoscopic or robotic assisted laparoscopic sacrocolpopexy depending upon their clinical evaluation. The participants will then be randomized to either Y mesh or dual flat mesh sacrocolpopexy according to a computer-generated randomization schedule with random block sizes with the use of the SAS statistical software package (SAS Institute, Cary, NC). Randomization will be carried out by provider. All patients will be blinded to their assignment.

Office Interventions

In addition to a standardized evaluation including the history and physical examination, patients will be asked to complete the Pelvic Floor Distress Inventory (PFDI-20) questionnaire at the pre-operative visit as well as the 6 week, 6, 12 and 24 month postoperative visit. Completion of these questionnaire is the only additional assessment that is specific to participation in this study and is not usually included as part of the standard care of sacrocolpopexy. It should take no more than 10-15 minutes to complete the questionnaire. The study subjects will not be exposed to any additional risk by participating in this study except for the inconvenience of completing the questionnaire.

Surgical Interventions

Laparoscopic sacrocolpopexy will be performed using four ports: an umbilical port for the laparoscope, two ports (either 5 or 10/12 mm) in the bilateral lower quadrants, and one 5-mm port placed at the level of the umbilicus, lateral to the rectus muscle on either side for retraction. The robotic-assisted hysterectomy will be performed using the da Vinci Surgical System (Intuitive Surgical Inc., Sunnyvale, CA, USA) using five ports: a 12mm umbilical port for the laparoscopic, two 8 mm robotic ports placed 2cm inferior and 9-10cm lateral to the umbilicus bilaterally, an 8mm robotic port placed in the left axillary line at the level of the umbilicus, and a 8mm or 10/12mm accessory port either in the right upper quadrant approximately 3cm distal from the costal margin, or in the right lower quadrant, 2cm above and medial to the anterior superior iliac spine.

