All paper forms used for data collection will be kept in a research cabinet dedicated to this project which will be locked at all times, in a locked office at the Cleveland Clinic. All forms will contain de-identified information – identification numbers will correspond to the subjects listed in the master excel file.

All study data will be transferred and managed electronically using REDCap (Research Electronic Data Capture). Each subject will be entered into REDCap using the assigned identification number from the master excel file. REDCap is a secure, web-based application designed to support data capture for research studies, providing user-friendly web-based case report forms, real-time data entry validation, audit trails, and a de-identified data export mechanism to common statistical packages. The system was developed by a multi-institutional consortium which was initiated at Vanderbilt University and includes the Cleveland Clinic. The database is hosted at the Cleveland Clinic Research Datacenter in the JJN basement and is managed by the Quantitative Health Sciences Department. The system is protected by a login and Secure Sockets Layers (SSL) encryption. Data collection is customized for each study as based on a study-specific data dictionary defined by the research team with guidance from the REDCap administrator in Quantitative Health Sciences at the Cleveland Clinic.

Analysis Plan:

There will be 4 arms to this study: laparoscopic (robotic-assisted and conventional) sacrocolpopexy with Y mesh and laparoscopic (robotic-assisted and conventional) sacrocolpopexy with dual flat mesh. Subjects will be chosen based on surgeon preference to either undergo RA LSC ASC or conventional LSC ASC. They will then be randomized to either a Y mesh arm or a Dual Mesh arm. We determined that 9 subjects in each arm were needed to detect a difference of 30 minutes or more in suturing time between the two groups with 80% power and a significance level of .05. We will account for potential subject drop out and loss to follow-up as well as unforeseen factors in recruiting and will plan to recruit 15 subjects to each arm, for a total of 60 subjects.

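### The plan sets 15 subjects in each of four mesh-by-route arms, but the randomisation described does not ensure that cell size or mesh balance within route

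*Combined protocol and SAP*

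**What the plan says.** The Analysis Plan opens with "There will be 4 arms to this study": Y mesh and dual flat mesh, each by robotic-assisted and by conventional laparoscopy. On size it says "We determined that 9 subjects in each arm were needed". The target is a 30-minute difference in suturing time, at 80% power and a 0.05 level. Allowing for drop-out and recruitment problems, the investigators "will plan to recruit 15 subjects to each arm, for a total of 60 subjects".

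The same section says how route is set: "Subjects will be chosen based on surgeon preference to either undergo RA LSC ASC or conventional LSC ASC". The Randomization section agrees that the surgeon fixes the route before mesh is allocated. Mesh is then assigned from a computer-generated schedule with random block sizes, and "Randomization will be carried out by provider". No other factor is named, and no section gives a separate schedule, quota or cap for each route.

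Route is used later. The Analysis Plan compares the meshes pooled over route and specifies a two-way ANOVA with two categorical factors. Secondary Outcomes lists "Hospital costs (Y mesh v. dual mesh and stratified by RA LSC v. LSC". Surgical Interventions has a different suturing and knot-tying technique for each route, so route is plausibly related to suturing time.

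**The concern.** Four arms of 15 require two things: 30 robotic and 30 conventional cases, and a 15:15 mesh split inside each route. Random blocks control the overall mesh split, and the split within provider if provider is a stratum. They control neither the number of cases in each route nor the mesh split within a route, unless route is a stratum or each provider keeps to one route. The documents state neither.

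Two things are at stake. A reader will take 15 v 15 per route as a feature of the design, when the plan has no written mechanism for it. And results reported within route, such as costs, may rest on cells much smaller than 15, possibly smaller than the 9 that the plan itself calls the minimum per arm.

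**Working it through.** **Inputs from the Analysis Plan.** 4 arms; 15 per arm; 60 in total; minimum 9 per arm; difference 30 minutes; power 80%; significance level 0.05. The SD, the sidedness of the test and the drop-out rate are not given.

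**Assumptions, not in the documents.** Robotic share 50%, 40%, 30% or 20%; 4 to 6 providers who each use both routes; permuted blocks of 2 and 4, or of 2, 4 and 6.

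**1. The plan's own figures.** 15 × 4 = 60 is correct. Going from 9 to 15 equals 9/(1 − 0.40), an implied allowance of 40%. The 9 cannot be confirmed without an SD. With n = 2·SD²·(1.960 + 0.842)²/30² (two-sided), rounding up to 9 needs an SD of about 21.4 to 22.7 minutes; with the t distribution it is about 20.0 to 21.3. I use 21.4 below, which gives 80% power at 9 v 9.

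**2. Cell size when route is the surgeon's choice.** The expected cell in the less-used route is 60 × share / 2. The number of cases in that route is taken as binomial(60, share). Fewer than 18 cases makes 9 + 9 impossible.

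| Share of less-used route | Expected cell | P(exactly 30/30) | P(fewer than 18 cases) |
|---|---|---|---|
| 50% | 15 | 10% | 0.05% |
| 40% | 12 | 3% | 4% |
| 30% | 9 | 0.05% | 45% |
| 20% | 6 | under 0.001% | 96% |

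Chance variation in mesh within route adds to this. With provider-only blocks, the smallest of the four cells is below 9 in about 3% of simulated trials at a 50% share, 19% at 40%, 68% at 30% and 99% at 20% (4 providers, blocks of 2, 4 and 6). At 50%, all four cells equal 15 in about 1%.

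**3. Mesh balance within route.** At a 50:50 route mix with provider-only blocks, the mesh counts differ by 6 or more within a route (such as 12 v 18) in about 20–23% of simulated trials. With provider-by-route blocks this is 0.1–1.7%. As a check without blocks, the hypergeometric probability of a 12:18 split or worse among 30 robotic cases, with 30 of 60 patients on each mesh, is 19.6%.

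**4. What imbalance costs.** The standard error of a within-route contrast is proportional to √(1/n₁ + 1/n₂). For 15 v 15 this is 0.365 and for 12 v 18 it is 0.373, a rise of 2.1%. Two-sided t power for 30 minutes at SD 21.4:

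| Cells | Power |
|---|---|
| 15 v 15 | 96% |
| 12 v 18 | 95% |
| 10 v 20 | 94% |
| 9 v 9 | 80% |
| 6 v 6 | 59% |

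Uneven mesh within route costs little; small cells cost much more. The pooled 30 v 30 comparison has power above 99% at the same SD.

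**5. What stratifying repairs.** At a 30% share (4 providers, blocks of 2, 4 and 6), the smallest cell is below 9 in 68% of runs with provider-only blocks, 56% with provider-by-route blocks and 48% with route-only blocks. A within-route mesh difference of 4 or more occurs in 44%, about 15% and 0% of runs. Stratifying improves balance but leaves cell size to the route mix.

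**The case against.** The strongest reply is that 15 per arm is worded as a recruitment plan, not a promise. It implies 30 per route, and a site could meet that by closing a route once full. This stands in part: the sizes may come about, so the design fails to ensure them rather than making them impossible. But no such limit is written.

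Second, the main comparison pools the routes, mesh remains randomised, and the two-way ANOVA can carry route. A reader might infer that the mesh comparison is biased or underpowered. The documents do not support that. Chance imbalance after randomisation is not bias, ordinary standard errors allow for it, and the pooled power is ample at the SD implied by the plan's own figure. One reservation is that the ANOVA sentence does not name its two factors. The sentence on controlling for route names logistic regression, which does not suit a continuous time or cost.

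Third, the simulations rest on invented inputs. That is correct. In particular, if each surgeon kept to one route, provider blocks would already nearly balance mesh within route: a difference of 4 or more occurs in 1.5% of runs with 4 providers. The documents do not say that surgeons do so, and cell size would still be uncontrolled.

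Finally, stratifying by provider and adjusting for route in the analysis is a defensible design. That holds for the pooled comparison. It does not support stating the size as 15 in each of four arms.

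**Conclusion.** The point holds as a gap between the stated size and the randomisation described. Nothing written ensures 15 per mesh-by-route cell or balanced mesh within route. The consequence for the main suturing-time comparison is small, provided route is a factor in the model. The consequence for within-route results, including the stratified costs, depends on the route mix: negligible near 50:50, material at about 30:70, and severe at 20:80. The documents give no expected mix, so these figures are illustrations under assumed provider numbers, block sizes and route shares; the power figures also rest on the assumed SD of 21.4 minutes. The change is worth making because it is cheap and route is known before allocation, but the trial's main conclusion does not hang on it.

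**What to change.** 1. Restate the sample size as 30 per randomised mesh group. Say that the route split follows surgeon choice, so 15 per mesh-by-route cell is a target that is not guaranteed. If the investigators do want 15 per cell, a written recruitment limit of 30 per route is also needed.
2. Generate the schedule with route as a stratum within provider, using small random blocks, and say whether provider is meant as a stratum or as the person who carries out the randomisation.
3. Name mesh and route as the two ANOVA factors, and keep route in the analysis.

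The cost is a regenerated randomisation list and a few sentences, with no extra patients for items 1 to 3. The downside is more and smaller strata, with some incomplete blocks. A limit of 30 per route, if chosen, could lengthen recruitment.

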- The stem portion of the graft is then brought to the sacral promontory and sutured to the anterior longitudinal ligament using 2 permanent (prolene) No. 0 sutures. The excess mesh is then trimmed.

2. Restorelle dual flat mesh: 2 pieces of 15 x 4 cm mesh

- One mesh arm is introduced into the pelvis through one of the ports.
- The arm is fixed to the anterior or posterior vaginal wall using 5 delayed- absorbable (PDS) No. 2-0 sutures in an interrupted fashion, 1 to 2 cm apart from each other.
- The second mesh arm is then introduced into the pelvis through one of the ports.
- The arm is fixed to either the anterior or posterior vaginal wall, depending on where the first arm was placed, using 5 delayed- absorbable (PDS) No. 2-0 sutures in an interrupted fashion, 1 to 2 cm apart from each other.
- The two arms are then brought to the sacral promontory and sutured together to the anterior longitudinal ligament using 2 permanent (prolene) No. 0 sutures. The excess mesh is then trimmed.

The peritoneum is then closed over the exposed graft with absorbable suture.

Routine cystoscopy will also be performed in order to assess for lower urinary tract injury. A vaginal exam is performed, and an anterior and/or posterior colporrhaphy and perineorrhaphy are performed if needed. Anti-incontinence procedures may also be performed if needed.

**In laparoscopic cases, all suturing will be done extracorporeally while intracorporeal knot-tying technique will be performed in robot assisted laparoscopic cases.

Data Collection & Management:

Preoperative data will include the following:

- Patient age, race, vaginal parity, menopausal state, BMI, prior prolapse surgery, preoperative prolapse stage
- PFDI-20
- Labs (Hb/Hct)

Data points recorded during the procedure will include:

- Total OR time = operating room time of entry and exit
- Total Case time = time from incision to closure
- Total Suturing time = time from insertion of Y mesh or first flat mesh arm into pelvis to last sacral suture placed
- Level of surgeon performing suturing: Attending v. Fellow v. Both
- Concomitant procedures
 - Hysterectomy – Supracervical or Total
 - Anterior Colporrhaphy
 - Posterior Colporrhaphy
 - Perineorrhaphy
 - Midurethral Sling
- Estimated blood loss
- Intraoperative complications
 - EBL > 500cc
 - Vascular Injury
 - Cystotomy
 - Ureteral Injury
 - Bowel Injury - small bowel, large bowel, rectal

Postoperative data will include the following:

- Days in the hospital

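### Route is to be controlled by a logistic regression although all three primary outcomes are times; and if randomisation is stratified by provider, no stated model names provider

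*Combined protocol and SAP*

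**What the plan says.** Under Primary Outcomes, the protocol lists suturing time, operating room time and case time. All are elapsed times, and the sample size in the Analysis Plan is set on a 30-minute difference in the first.

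The Analysis Plan then makes these statements:

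- On layout: "There will be 4 arms to this study", formed by crossing mesh with route (conventional or robotic-assisted). Route is the surgeon's choice; mesh is randomised afterwards.
- On the contrast: mesh types are "compared between the two groups (Y mesh LSC + RA LSC v. Dual mesh LSC + RA LSC", that is, pooled over route.
- On the test: "With a continuous outcome and two categorical independent factors, a two-way" ANOVA will be used. Its two factors are not named.
- On estimation: "A linear regression will be done to demonstrate actual changes in surgical time attributed to each variable". The variables are not listed.
- On route: "We will control for LSC ASC and RA LSC ASC by performing a logistic regression". No dependent variable is given.

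The Randomization section describes a "computer-generated randomization schedule with random block sizes" and adds "Randomization will be carried out by provider". The Analysis Plan does not mention provider.

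**The concern.** The one sentence that names a method for controlling route names one that does not fit the primary outcomes. Logistic regression models the log-odds of a binary event. Applied to a time cut at some value, it discards information and answers a different question. Applied with route as the outcome, it does not estimate a mesh effect on time at all. An analyst must either set aside a written instruction or guess what it was for.

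Route is worth adjusting for on the protocol's own text. Surgical Interventions states: "In laparoscopic cases, all suturing will be done extracorporeally while intracorporeal knot-tying technique will be performed in robot assisted laparoscopic cases". That difference falls inside the interval that defines suturing time.

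Provider is a related but separate gap. If the schedule is stratified by provider, an analysis that ignores provider leaves between-provider variation in the residual, although the design has already balanced mesh against it. The standard error is then too large. What is at stake is precision and a clear rule, not bias: mesh is randomised after route is chosen, and stratification would balance it within provider.

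**Working it through.** **1. Does the named method fit?** The three primary outcomes are in minutes; a logistic coefficient is a log-odds ratio. In one simulated trial (60 patients, SD 20, route shift 20, true mesh effect −30 minutes), a linear model with mesh and route estimated −26.4 minutes. A logistic model of time above the median gave −1.88 on the log-odds scale, which is not a difference in minutes.

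**2. Is route handled elsewhere?** The four arms are mesh by route, and the sentence just before the ANOVA groups patients by those two variables. They are its evident factors. A linear regression on them gives a route-adjusted difference in minutes, and the loss is then zero.

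**3. The plan's own figure.** Nine per arm for 30 minutes, 80% power and 0.05 cannot be reproduced, because no SD is stated. Solving backwards (noncentral t, two-sided assumed):

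- 9 v 9 reaches 80% at SD 21.32, and 8 v 8 at SD 19.91, so nine per group fits an SD of about 19.9 to 21.3.
- Nine in each of four arms, pooled to 18 v 18, gives SD 31.21.
- The sidedness is not stated. One-sided, nine per group fits about 22.9 to 24.5.

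**4. Hypothetical: route left out.** Assume 60 patients (15 × 4), 30 per mesh, half on each route, and a route shift of δ minutes.

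- With route: half-width = t(0.975, 57) × SD × √(2/30) = 2.0025 × SD × 0.2582.
- Without route: residual variance = (58 SD² + 60 δ²/4)/58 on 58 df.
- Example, SD 21.32 and δ = 20: 454.5 + 6000/58 = 558.0, root 23.62. Half-width = 2.0017 × 23.62 × 0.2582 = 12.21, against 11.02 with route (+10.8%).

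| SD | With route | Without, δ = 10 | δ = 20 | δ = 30 |
|---|---|---|---|---|
| 19.91 | 10.29 | 10.62 (+3.2%) | 11.56 (+12.3%) | 12.96 (+25.9%) |
| 21.32 | 11.02 | 11.33 (+2.8%) | 12.21 (+10.8%) | 13.55 (+22.9%) |
| 31.21 | 16.14 | 16.34 (+1.3%) | 16.97 (+5.1%) | 17.95 (+11.3%) |

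**5. Provider, only if stratified.** Simulation with assumed inputs: SD 21.3, 60 patients, permuted blocks of 2, 4 or 6 within provider, 4 or 8 providers, route shift 20, no mesh effect, 6,000 replicates. Entries are mean 95% half-widths in minutes, without v with provider, then the rejection rate of the nominal 5% test without provider.

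| Between-provider SD | 4 providers | 8 providers |
|---|---|---|
| 5 | 11.28 v 11.08; 4.6% | 11.35 v 11.23; 4.6% |
| 10 | 11.96 v 11.11; 3.7% | 12.11 v 11.22; 3.3% |
| 20 | 14.15 v 11.12; 2.0% | 14.71 v 11.19; 1.6% |

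With provider in the model, rejection was 4.6% to 5.4%. These rates carry simulation error: repeat runs for a between-provider SD of 10 to 20 put the rate without provider anywhere from 1.6% to 4.4%.

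The price of including provider when providers do not differ (2,500 replicates per setting) is a mean widening of 0.2% to 0.5% with 4 providers and 1.0% to 1.9% with 8. If the strata were provider by route, the means reach 0.7% and 2.7%.

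**6. Can all three terms be fitted?** If each provider uses only one route, route is a function of provider. With 4 providers the design matrix has 6 columns and rank 5. The route coefficient is then not separately estimable; the mesh difference still is.

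**The case against.** The strongest reply is that route is already dealt with. The ANOVA and regression come before the disputed sentence, fit a continuous outcome, and on any natural reading include mesh and route. That stands, and it limits the point. A reader might infer that the plan has no usable route adjustment, or that the primary comparison is invalid or biased. The documents do not support that. What remains is an instruction that is wrong for the times, next to two models whose terms are never listed. It may have been intended for complications, a secondary outcome, but it does not say so.

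A reader might also infer that a stratification factor has definitely been omitted. That goes too far. Alongside a blocked computer-generated schedule, stratification is the likely meaning of the provider sentence, but it could mean that the provider performs the randomisation. Since the regression variables are not listed, provider is unnamed rather than excluded.

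Finally, the documents give no SD, route effect, number of providers, block sizes or between-provider SD. The figures above are therefore illustrations and not estimates of what this trial will lose. That objection stands too.

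**Conclusion.** The point holds in a limited form. The logistic sentence cannot deliver a route-adjusted difference in minutes and should be replaced. The primary mesh comparison is neither lost nor biased.

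For route, the effect is nil if the ANOVA contains it. Otherwise it cannot be determined from the documents; about 1% to 26% wider is an illustration for an SD of about 20 to 31 minutes and a route shift of 10 to 30 minutes.

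For provider, the point is conditional on stratification. Under the assumed inputs, leaving provider out costs little at a between-provider SD of 5 minutes and matters more at 10 to 20. The cost of including it unnecessarily is small throughout. Confidence is high on the logistic sentence and lower on provider until the sponsor clarifies. Minor to moderate, affecting clarity and precision.

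**What to change.** Replace the logistic sentence in the Analysis Plan with:

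> For each of total suturing time, total OR time and total case time, a linear model with mesh, route and, if randomisation is stratified by provider, provider will give the adjusted mean difference in minutes (Y minus dual flat) with its 95% CI. The ANOVA table will come from the same model. Logistic regression will be used only for binary outcomes such as complications.

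State in the Randomization section what the provider sentence means. If it is not stratification, the model is mesh plus route.

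Keep any further regression on other recorded variables, such as surgeon level and concomitant procedures, as a secondary analysis, so that the replacement does not shut out what the existing regression sentence may have been meant to cover. Add a note that if each provider uses only one route, no separate route coefficient will be reported, while the mesh difference remains estimable.

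The cost is a few sentences and one clarification, with no new data or patients. Including provider uses one degree of freedom per additional provider, at most, and brings slight imbalance from incomplete blocks: about 0.2% to 2% mean widening with 4 to 8 providers (up to 2.7% if strata are provider by route), before any gain in precision.
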